#### 14.1 Disposition

The number of ‘Subjects Screened’ will be summarized by country and site along with the number and percentages of ‘Subjects Re-Screened’, ‘Screening Failures’, and ‘Randomized Subjects’ with percentages based on the SCR.

The reasons for screen failures will be summarized on the SCR showing the number of subjects screened, the number of screen failures, the number of subjects re-screened, the number of re-screen failures and the primary reason for screen failure (the last screen failure in case of re-screen). A listing will display the reason for (the last) screen failure and the date of (the last) screen failure. A separate listing will display the inclusion/exclusion criteria not met of screen failures for which the reason is “not eligible per inclusion/exclusion criteria”.

The disposition of the randomized subjects will be summarized on the FAS by study treatment status and study completion status as detailed in Section 7.1 (without counts of screened subjects, re-screened subjects and screen failures). In the event of randomized subjects having not started study treatment, the summary will provide the list in a footnote.

The disposition of treated subjects will be summarized similarly on the SAF (without counts of screened subjects and randomized subjects). In the event of randomized subjects taking the incorrect treatment, the summary will provide the list of subjects that have switched treatment groups compared with the mFAS.

Subjects unblinded during study (if any) will be detailed (event that triggered the request, action taken following the unblinding) in a listing.

Subjects discontinuing treatment permanently will be summarized on the mFAS and the SAF, by treatment and overall along with reasons for discontinuing study treatment. This summary will be repeated for study treatment discontinuations related to the COVID-19 pandemic.

Subjects withdrawing from the study early will be summarized on the FAS, by treatment and overall along with the reasons for withdrawal from the study. This summary will be repeated for study discontinuations related to the COVID-19 pandemic.

Eligibility criteria not met will be summarized on the FAS by treatment and overall. Eligibility criteria not met will also be summarized on the subset of the SCR of screen failures not eligible as per inclusion/exclusion criteria.

Protocol deviations will be summarized on the FAS, by treatment and overall, by protocol by category, sub-category (ordered according to the first 3 digits of the deviation identifier). Important protocol deviations (DV.DVGRPID = IMPORTANT) will be summarized the same way.

The summary of protocol deviations and important protocol deviations will be repeated for deviations related to the COVID-19 pandemic.

The number and percentage of ‘Subjects included’ in each analysis set will also be summarized with percentages based on the relevant set: (FAS for mFAS, mFAS-GIS, and PPS; SAF for PK through set and PK sub-study set). A separate table will provide, for each analysis set, the number and percentage of subjects excluded by reason for exclusion.

Subjects with a start of treatment date not matching the randomization date of the IRT system will be listed.

## **14.2 Demographics and baseline characteristics**

Demographics and baseline characteristics will be summarized on the FAS, mFAS (if it differs by at least 5 subjects), PPS, and mFAS-GIS populations, by treatment and overall, first based on all subjects and then by sex.

The country will be displayed using the ISO 3166 short name lower case, omitting “(the)” if present in the short name.

## **14.3 Analysis of stratification variable**

In the event of discrepancies between the IRT system and the eCRF, each of the two stratification variables will be summarized (on the mFAS, PPS, and mFAS-GIS populations, by treatment and overall) in categories for both the IRT-assigned value and the value reported in the eCRF. In addition, shift tables of ERT status at screening according to eCRF (table rows) by ERT status at screening according to IRT (table columns) will be prepared for each treatment group and overall, first based on all subjects

and then separately for each sex (according to eCRF). Otherwise, the stratification variables will be summarized only once.

The stratum information recorded in the IRT system will be decoded from the leading digit of the randomization number (DS.DSREFID) as follows:

- 1: Sex = M, ERT at screening = “switch”
- 2: Sex = M, ERT at screening = “pseudo-naïve” / “treatment naïve”
- 3: Sex = F, ERT at screening = “switch”
- 4: Sex = F, ERT at screening = “pseudo-naïve” / “treatment naïve”.

The ERT status at screening according to the eCRF will be determined by checking the medication in the CM dataset where CM.CMCAT = “PREVIOUS FABRY DISEASE SPECIFIC THERAPY” and (CMCLAS=“ENZYMES” or CMDECOD in [“PEGUNIGALSIDASE ALFA”, “MOSS-AGAL”]) and the corresponding end date (CM.CMENDTC [possibly incomplete] vs the screening date [last screening in the event of re-screening]). In the event of missing end date, ERT status will be presumed to be “switch”.

#### **14.4 Baseline disease characteristics**

Baseline disease characteristics will be summarized on the FAS, mFAS (if it differs by at least 5 subjects) PPS, and mFAS-GIS populations, by treatment and overall.

#### **14.5 Exposure**

The duration of exposure to study treatment will be presented as a continuous variable on the SAF, by treatment and overall. In addition, the cumulative distribution by different class intervals (i.e., at least 1 month, at least 2 months, at least 3 months, and so on up to 6 months, defining a month as 365.25/12 days) will be tabulated to show counts and percentages of subjects in each class interval.

The sum of duration of exposure across all subjects in years will be displayed as subject year exposure.

The mean daily dose (mg) will also be presented as a continuous variable.

#### **14.6 Efficacy observation period and PTOP**

The duration of the efficacy observation period and of the PTOP will be presented as a continuous variable on the mFAS, by treatment and overall.

#### **14.7 Drug accountability**

Study treatment dispensing and accountability data collected in the eCRF will be presented in subject listings without any further summarization.

## 14.8 Study treatment compliance

The eDiary-based study treatment compliance will be summarized overall and by period (V2 to V3, V3 to V4, V4 to V5, V5 to V6, V6 to V7, and V7 to V8).

The study treatment compliance according to the study treatment log will be summarized in the same way.

## 14.9 FD history

The FD history will be summarized on the FAS, mFAS (if it differs by at least 5 subjects) populations, by treatment and overall, first based on all subjects and then by sex.

Neuropathic pain symptoms with pre-specified answer “Other” ticked (record in SUPPMH with QNAM=PAINOTH) will be reported in summary tables on common row “Other”, further details (free text in SUPPMH.QVAL) being reported in a listing. Neuropathic pain symptoms(s) triggering factors with pre-specified answer “Other” ticked (1 record in FAMH with FAORRES with FAOBJ = Other neuropathic symptoms) will be reported in summary tables on a single common row “Other”, further details (free text in FAMH.FAORRES) being reported in a listing.

Other FD-related symptoms and complications will be summarized first including all symptoms and complications (previous and current) and then restricting the summary to current medical symptoms and complications. A medical symptom/complication will be retained as current if not being answered “No” to question “Ongoing at Screening” (i.e., MH.MHENRTPT = ONGOING or missing). Symptoms within a pre-specified category with the pre-specified answer “Other” ticked (MH.MHGRPID = OTHER) will be reported in summary tables on a single common row labelled “OTHER” with a breakdown by preferred term within their respective pre-specified category, further details (verbatim term: MH.MHTERM) being reported in a listing. Symptoms entered in the pre-specified category “OTHER” (MH.MHSCAT = OTHER) will be reported in summary tables within the category “OTHER” with the free text entered by the investigator (MH.MHTERM) reported in a listing.

The history of ERT infusion reaction will be summarized by system organ class (MH.MHBODSYS) and preferred term (MH.MHDECOD) in two separate tables: one for subjects with switch ERT status at screening and one for subjects with (pseudo-)naïve ERT status at screening.

The historical eGFR slope will be summarized as a quantitative variable.

## 14.10 Medical history (other than FD)

Diseases and procedures will be summarized on the FAS, mFAS (if it differs by at least 5 subjects) populations, by treatment and overall, by system organ class (SOC) and preferred term, first including all medical conditions (previous and current) and then restricting the summary to current medical conditions. A medical condition will be retained

as current if not being answered “No” to question “Ongoing at Screening” (i.e., MH.MHENRTPT = ONGOING or missing).

#### **14.11 Previous and concomitant medications**

Study treatment concomitant medications (other than FD-specific therapy) at baseline, study treatment concomitant medications, and study concomitant medications will be summarized on the SAF, by treatment and overall, by Anatomical Therapeutic Chemical class and preferred name.

Study treatment concomitant pain medications at baseline, study treatment concomitant pain medications, and study concomitant pain medications recorded in the eDiary will be summarized on the SAF, by treatment and overall, by Anatomical Therapeutic Chemical class and preferred name.

Previous FD-specific therapies will be summarized as well.

Initiation (or re-initiation) of ERT during study will be summarized by ERT status at baseline and overall.

### **15 EFFICACY ANALYSIS**

#### **15.1 Overall testing strategy**

[figure not shown]
Comparisons of lucerastat vs placebo will be conducted for the primary and secondary endpoints assessed at Month 6.

The Type I error rate will be controlled at a two-sided alpha of 5% for the testing of the four null hypotheses associated with the primary and secondary endpoint comparisons employing a fixed-sequence statistical testing strategy in the following order:

1. Change from baseline to Month 6 in the “modified” BPI-SF3 score of “neuropathic pain at its worst in the last 24 hours”.
2. Change from baseline to Month 6 in plasma Gb3.
3. Change from baseline to Month 6 in the NRS-11 score of “abdominal pain at its worst in the last 24 hours” in subjects with GI symptoms at baseline.
4. Change from baseline to Month 6 in the number of days with at least 1 stool of a BSS consistency Type 6 or 7 in subjects with GI symptoms at baseline.

The order of the fixed-sequence statistical testing strategy is depicted in [Figure 2](#). In the event that the null hypothesis is not rejected for an endpoint in the sequence, claims for statistical significance cannot be made for endpoints that follow in the sequence.

**Figure 2 Fixed-sequence statistical testing strategy**

The primary hypothesis related to  $H1_0$  is initially assigned the local two-sided statistical significance level  $\alpha = 0.05$ , whereas  $H2a_0$  through  $H2c_0$  from the secondary family of endpoints are assigned the local statistical significance level 0. If  $H1_0$  is rejected, the local statistical significance level  $\alpha$  is passed on to  $H2a_0$  and so on as long as hypotheses are rejected.

## 15.2 Analysis of the primary efficacy variable

### 15.2.1 Hypotheses

Hypotheses for the primary endpoint are formulated in terms of the mean difference in change from baseline to Month 6.

$$H1_0: \text{lucerastat} - \text{placebo} = 0$$

is the null hypothesis that there is no difference between treatments.

$$H1_A: \text{lucerastat} - \text{placebo} \neq 0$$

is the alternative hypothesis that a difference in change from baseline to Month 6 exists between treatments.

### 15.2.2 Description of missing data

All available eDiary data collected from baseline (last four weeks prior to randomization), and after randomization and up to the Month 6 visit (i.e., during the treatment phase, after treatment discontinuation and during the FU and PTOP periods) will be used to calculate the monthly scores. All the data up to the Month 6 visit will be included in the primary analysis.

Despite the measures implemented to prevent missing data [described in protocol section 7.2.2.2.4], some missing data will occur in the daily measurements, possibly translating into missing monthly scores. In the next sections “missing data” will refer to missing monthly scores.

A summary of missing patterns can be presented for each treatment group as illustrated in [Table 10](#).

**Table 10 Example: Summary of patterns of missingness**

Pattern	Month 1	Month 2	Month 3	Month 4	Month 5	Month 6	N (%)
1	X	X	X	X	X	X	xx (xx.x%)
2	X	X	X	X	X	-	xx (xx.x%)
3	X	X	X	-	X	-	xx (xx.x%)
4	X	X	X	X	-	-	xx (xx.x%)
5	X	X	X	-	-	-	xx (xx.x%)

### 15.2.3 Primary statistical analysis

The primary analysis will be performed on the mFAS, according to the intent-to-treat approach. All available data will be used regardless of occurrences of ICEs, such as premature treatment discontinuation or changes in background medication.

The null hypothesis will be tested using the two-sided significance alpha level = 0.05, using the following method.

The observed data cannot be used to distinguish between missing at random (MAR) and missing not at random (MNAR) missing data mechanisms [NRC Report 2010] and in incomplete-data settings a definitive MNAR analysis does not exist [Molenberghs 2004].

An analysis based on a pattern-mixture model will be performed using a MAR imputation in the placebo arm while using a MNAR approach in the lucerastat arm: missing data will be imputed applying a control-based multiple imputation (MI) assuming MNAR using the CR approach [Carpenter 2013]. Instead of imputing a single value for each missing observation, a set of values is generated from the model, resulting in as many distinct complete datasets without missing data. The imputation model includes the baseline value, the two stratification factors (sex and ERT treatment status at screening) and all post-baseline monthly scores up to Month 6. Missing data for subjects from both treatment arms will be imputed using data from the placebo arm. This approach assumes that subjects with missing data in the lucerastat arm have outcomes trending towards outcomes observed in the placebo arm, i.e., the imputations result in a treatment effect that gradually diminishes towards the placebo arm.

More specifically, the imputations will be performed in two steps: “intermittent” missing data (a monthly score is missing but one or more monthly score[s] is [are] available in following month[s]) will be first imputed by a Markov chain Monte Carlo method using a non-informative Jeffreys prior, thus creating 500 partially imputed “monotone” datasets; then, the remaining missing data will be imputed once in each of these 500 “monotone” imputed datasets using the CR approach leading finally to 500 complete imputed datasets. Imputed values will be restricted to remain in the clinically relevant range of [0, 10].

The two-step MI procedure will be implemented by the following SAS® code:

```

proc mi data=h nimpute=500 seed=32767 minimum = . . . . 0 0 0 0 0 0 maximum = . . . . 10
10 10 10 10 10 minmaxiter= 1000000out=h2;
  mcmc impute = monotone;
  var treatment sex ertstatus baseline y1 -- y6;
run;
proc mi data=h2 nimpute=1 seed=32767 minimum = . . . . 0 0 0 0 0 0 maximum = . . . . 10
10 10 10 10 10 minmaxiter=1000000out=h3;
  by _imputation_;
  class treatment sex ertstatus;
  var sex ertstatus bsl y1 -- y6;
  mnar model (y1 -- y6 / modelobs=(treatment="placebo"));
  monotone regression;
run;

```

An analysis of covariance (ANCOVA) model will then be used to analyze this endpoint on each imputed dataset. The following terms will be included in the model: baseline value, the two stratification factors (sex and ERT treatment status at screening), and the treatment group. This analysis will be implemented by the following SAS® code:

```

proc mixed;
  by _imputation_;
  class sex ertstatus treatment;
  model change = sex ertstatus bsl treatment;
  lsmeans treatment / cl pdiff;
run;

```

Uncertainty in the imputations will be reflected appropriately in the analysis by combining the results on each imputed dataset using Rubin's methodology [Rubin 1987]. The final estimate is the mean of the 500 per-imputation estimates and the final variance is the sum of the average within-imputation variance and  $(1 + 1 / 500)$  times the between-imputation variance [Rubin 1987]. From the final point estimate and variance, the 95% CI will be determined.

The results aggregation of the MI procedure after analysis of the 500 complete datasets will be implemented by the following SAS® code:

```

proc mianalyze data = <ods output lsmeans from proc mixed>;
  ods output parameterestimates=ls_m_comb;
  by treatment;
  modeleffects estimate;
  stderr stderr;
run;

proc mianalyze data = <ods output diffs from proc mixed>;
  ods output parameterestimates=diff_comb;
  modeleffects estimate;
  stderr stderr;
run;

```

The mean difference in changes from baseline to Month 6 between lucerastat and placebo together with its two-sided 95% CI and p-value will be reported.

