#### 15.2.4.1 Model-based analysis relying on the MAR assumptions

Missing monthly modified BPI-SF3 scores will be imputed using a MI method [Rubin 1987] based on a model including the baseline modified BPI-SF3 score, stratification factors, all available post-baseline monthly scores up to Month 6, and treatment group. In contrast to the CR approach described in Section 15.2.3, treatment group is included in the imputation model and therefore missing data for subjects from the lucerastat arm will be imputed using data from the lucerastat arm.

The MI procedure will be implemented by the following SAS® code:

```
proc mi data=h nimpute=500 seed=32767 minimum = . . . . 0 0 0 0 0 0 maximum = . . . . 10
10 10 10 10 10 minmaxiter=1000000out=h2;
mcmc impute = monotone;
var treatment sex ertstatus baseline y1 -- y6;
run;
proc mi data=h2 nimpute=1 seed=32767 minimum = . . . . 0 0 0 0 0 0 maximum = . . . . 10
10 10 10 10 10 minmaxiter=1000000out=h3;
by _imputation_;
class treatment sex ertstatus;
var treatment sex ertstatus baseline y1 -- y6;
monotone regression;
run;
```

An ANCOVA model will then be used to analyze this endpoint on each imputed dataset as described in Section 15.2.3.

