### 15.3.3 Change from baseline to Month 6 in plasma Gb3

This absolute change endpoint will be analyzed using the mFAS. All available data will be used regardless of occurrence of ICEs such as premature treatment discontinuation or changes in background medication.

Missing data will be imputed applying an MI approach assuming MAR similarly to that described in Section 15.2.4.1. The imputation model includes the baseline value, the two stratification factors (sex and ERT treatment status at screening), Month 1, Month 3, Month 5, and Month 6 values and treatment group.

Subjects with the baseline value missing will be excluded from this analysis.

The MI procedure will be implemented by the following SAS® code:

```
proc mi data=h nimpute=500 seed=32767 min=. . . . 0 0 0 0 minmaxiter=1000000out=h2;  
  mcmc impute = monotone;  
  var treatment sex ertstatus baseline y1 y3 y5 y6;  
run;  
proc mi data=h2 nimpute=1 seed=32767 min=. . . . 0 0 0 0 minmaxiter=1000000out=h3;  
  by _imputation_;  
  class treatment sex ertstatus;  
  var treatment sex ertstatus baseline y1 y3 y5 y6;  
  monotone regression;  
run;
```

The MAR assumption can be considered reasonable for this endpoint as it is an objective assessment and not patient-reported and therefore less likely to be related to reasons for study withdrawal. In addition, patients, physicians as well as the sponsor are blinded to the plasma Gb3 results until after database lock and a lower amount of missing data is expected compared to the abdominal pain and stool consistency endpoints.

The analysis, within each imputed dataset, will be performed using an ANCOVA as described in Section 15.2.3.

Results from these analyses are combined using Rubin's methodology [Rubin 1987] implemented in SAS® PROC MIANALYZE.

The mean difference in changes from baseline to Month 6 between lucerastat and placebo together with its two-sided 95% CI and p-value will be reported.

To explore the robustness of inferences from the main analysis described above to deviations from its underlying assumptions regarding the nature of missing data, control-based MI assuming MNAR using the CR and J2R approaches [described in Sections 15.2.3 and 15.2.4.2] will be applied.

Subgroup analyses will be performed similarly to those described in Section 15.2.6 by including the respective subgroup and subgroup by treatment interaction in the ANCOVA.

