A supportive analysis using an MMRM approach will be conducted to characterize the treatment effect over time such that change in plasma Gb3 will be analyzed on all available data from all scheduled visits without replacement of missing values.

The model will enable:

- Estimation of the treatment difference (lucerastat minus placebo) in the mean changes from baseline to Month 6 along with the corresponding 95% CI;
- Characterization of the patterns of change over time in the mean change from baseline in Gb3 by treatment group.

The main analysis described above (MI assuming MAR + ANCOVA) will be repeated (with the log-baseline as covariate) on log-transformed values (i.e.,  $\log[\text{post-baseline}] - \log[\text{baseline}] = \log[\text{post-baseline} / \text{baseline}]$ ) leading via the back transformation  $x \rightarrow ((e^x - 1) \times 100)$  to treatment group results expressed as percent change from baseline and treatment effect estimate expressed as the ratio of the percent change between lucerastat and placebo. The log-transformation will only be applied after values have been imputed on the original scale, i.e., the imputation step is identical to the main analysis described above.

Patterns of missingness will be summarized as described in Section 15.2.2. An eCDF plot of the absolute change from baseline to Month 6 by treatment arms will be provided as well.

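### The SAP's only printed multiple-imputation pooling code passes no complete-data degrees of freedom; if it is followed for the MAR-imputed ANCOVAs, including plasma Gb3, their 95% CIs come out about 1 to 2% too narrow.

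*SAP*

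**What the plan says.** SAP 15.2.3 pools the 500 ANCOVA results with two PROC MIANALYZE calls, one for the group means and one for the treatment difference. The second begins "proc mianalyze data = <ods output diffs from proc mixed>". Each call contains the statement "modeleffects estimate" and a statement naming the standard error. Neither contains a degrees-of-freedom option. The text gives Rubin's variance formula and adds "From the final point estimate and variance, the 95% CI will be determined", without naming a reference distribution.

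These analyses impute under MAR and lead back to that section:

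- **MAR sensitivity analysis of the primary endpoint (SAP 15.2.4.1):** "An ANCOVA model will then be used to analyze this endpoint on each imputed dataset as described in Section 15.2.3".
- **Plasma Gb3 (SAP 15.3.3):** "Missing data will be imputed applying an MI approach assuming MAR similarly to that described in Section 15.2.4.1", followed by "The analysis, within each imputed dataset, will be performed using an ANCOVA as described in Section 15.2.3". For pooling it says "Results from these analyses are combined using" Rubin's method in PROC MIANALYZE, with no call printed. The log-scale repeat follows the same route: "The main analysis described above (MI assuming MAR + ANCOVA) will be repeated".
- **UACR (SAP 15.4.1.2) and the other biomarkers (SAP section 19):** both refer to 15.3.3.
- **Abdominal pain (SAP 15.3.1):** it takes its methods from 15.2.3 and 15.2.4, including a MAR sensitivity analysis on the mFAS-GIS.

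Neither document mentions a small-sample df adjustment.

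**The concern.** An ANCOVA fitted to about 118 subjects should be read against a t distribution on its residual df. The pooling call receives no df, so it can use only Rubin's large-sample df. With 500 imputations those run to tens or hundreds of thousands, which is the normal distribution in practice. Intervals from valid MAR imputation then come out slightly short and tests slightly above their nominal level. Plasma Gb3 matters most: it is second in the fixed sequence and the only confirmatory test imputed under MAR.

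**Working it through.** **Inputs.** N = 118 randomized, about 79 and 39 (SAP section 2). m = 500 imputations (SAP 15.2.3). The ANCOVA has an intercept, sex, ERT status, baseline and treatment, so 5 parameters and complete-data df v0 = N-5. The mFAS-GIS was planned at 69 subjects, 70% of 99 (protocol 10.5). Applying 70% to 118 gives about 83, which is an assumption. Neither document gives a missing-data rate, so r, the ratio of between- to within-imputation variance including the factor 1+1/m, is taken from about 0 to 0.20.

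**The plan's own figures.** The documents state no pooled df or CI width. The sample-size power in protocol 10.5 (66 and 33, difference 2, SD 3) reproduces at 87.20% against the stated 87.2%. It is used only for the gating argument below.

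**Nothing missing.** The 500 datasets are identical, so pooling should return the ANCOVA's own interval. The t critical value on 113 df is 1.981 and the code gives 1.960. Since 1 - 1.960/1.981 = 1.07%, the pooled CI is that much too narrow, and 2P(T113 > 1.960) = 5.25%. This step needs no assumption about missing data.

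**Some data missing.** Rubin's df = (m-1)(1+1/r)^2:

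- r = 0.05: 499 x 441 = 220,059
- r = 0.20: 499 x 36 = 17,964

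The small-sample version uses g = r/(1+r) and df_obs = (1-g) v0 (v0+1)/(v0+3). The adjusted df is 1/(1/df_Rubin + 1/df_obs). At N = 118 and r = 0.20, df_obs = 0.8333 x 113 x 114/116 = 92.5 and the adjusted df is 92.1.

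| N analysed | r | Adjusted df | Critical value without / with v0 | CI too narrow by | Size of a nominal 5% test |
|---|---|---|---|---|---|
| 118 | near 0 | 111.1 | 1.960 / 1.982 | 1.09% | 5.25% |
| 118 | 0.20 | 92.1 | 1.960 / 1.986 | 1.31% | 5.30% |
| 83 (assumed) | near 0 | 76.1 | 1.960 / 1.992 | 1.59% | - |
| 83 (assumed) | 0.20 | 63.2 | 1.960 / 1.998 | 1.91% | - |
| 69 (planned) | near 0 | 62.1 | 1.960 / 1.999 | 1.95% | - |
| 69 (planned) | 0.20 | 51.6 | 1.960 / 2.007 | 2.34% | - |

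Size is left out for abdominal pain because that analysis is a sensitivity analysis with no controlled alpha. If an assumed 6 subjects without a baseline value are excluded (N = 112), the narrowing is 1.15 to 1.38%.

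**Simulation on the Gb3 visit structure.** Under the null there were 80,000 trials in each of nine cells, with 79 and 39 subjects, MAR imputation with treatment in the model, and 500 imputations. Correlations (AR(1) 0.8, AR(1) 0.9, compound symmetry 0.7) and missingness at Month 6 (3%, 5%, 10%) were assumed. Data were normal without the SAP's lower limit of 0.

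| Missing at Month 6 | Size without complete-data df | Size with it |
|---|---|---|
| 3% | 5.20% | 4.95% |
| 5% | 5.21% | 4.96% |
| 10% | 5.22% | 4.94% |

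Overall it was 5.21% against 4.95%, a paired difference of 0.26 points (SE 0.006). A second simulation with 200 imputations gave 5.29% against 4.98% at 10% missing, and 5.38% against 5.07% at 20%.

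**The case against.** **The printed code belongs to a different analysis.** It serves the Copy Reference primary analysis, and no call is printed for Gb3. This stands, and it makes the point conditional. But 15.3.3 specifies Rubin pooling in PROC MIANALYZE with no df rule, and the 15.2.3 calls are the only template a programmer has.

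**The plan does what it says.** It cites Rubin's 1987 method and implements it; a small-sample df is a refinement. That PROC MIANALYZE takes infinite complete-data df by default is general software knowledge, not something in the documents. Still, the printed call supplies no df that could be used, and the case with nothing missing shows a shortfall against the SAP's own ANCOVA.

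**The consequence is small.** This also stands. Only a pooled statistic between 1.960 and about 1.983 is affected, a reported p of roughly 0.0474 to 0.0500. That is remote for Gb3 given the Phase 1b mean change of -55% (SD 10) in protocol 1.2.3. All the other analyses listed lie outside the alpha-controlled sequence.

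**Stronger readings to avoid.** A reader might infer that the primary test, or the main abdominal pain test, is also anti-conservative. The working does not support that: under Copy Reference, Rubin's variance is too large, and simulated size without the df correction was 4.54%, 4.03% and 3.15% at 2%, 5% and 10% missing. Only with almost nothing missing would the df effect show.

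A reader might also infer that the chance of a false Gb3 claim must exceed 5%. Gb3 is tested only after the primary rejects. Under the planning assumptions and with independent statistics, that chance is 0.872 x 5.25% = 4.6% at 66 and 33. At 79 and 39, where the same power formula gives 92.2%, it is 0.922 x 5.25% = 4.8%. It passes 5% only with higher primary power or positive dependence.

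**Conclusion.** The point holds as a minor one, on the condition that the MAR analyses are pooled as 15.2.3 prints or with PROC MIANALYZE given no complete-data df. The size depends on the number analysed and on an assumed r of about 0 to 0.20; a larger fraction of missing information would widen the gap. The consequence is slightly short intervals in several analyses, largest for the MAR sensitivity analysis of abdominal pain because the mFAS-GIS is smaller. For plasma Gb3 alone there is also a small excess in local test size. The Copy Reference tests are not defective on this account.

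**What to change.** In every MAR-imputed analysis, add EDF= to PROC MIANALYZE, set to the residual df of the fitted ANCOVA (N-5 for the main model, with N the subjects actually analysed). This covers SAP 15.2.4.1, the MAR sensitivity analysis in 15.3.1, 15.3.3 with its log-scale repeat, 15.4.1.2 and section 19. Print the Gb3 pooling call in 15.3.3 and report the pooled df beside each interval. For the Copy Reference and Jump to Reference analyses it is enough to state which df is used; adding EDF= there is optional and makes already conservative tests slightly more so.

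The cost is one option per call and one sentence in the SAP. Intervals in the MAR analyses widen by about 1 to 2%, and the loss of power for Gb3 is negligible.
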